9.3.2. Eliciting Adverse Events

The investigator or designee will ask patients about AEs by asking the following standard questions:

- How are you feeling?
- Have you had any medical problems since your last visit?
- Have you taken any new medicines since your last visit?

9.4. Study-Specific Adverse Event and Serious Adverse Event Reporting Instructions

9.4.1. Disease Progression

“Disease progression” (including fatal disease progression), which is expected in this study population and measured as an efficacy endpoint, should not be reported as an event term. Instead, the symptoms, signs, or clinical sequelae that result from disease progression should be reported as the event terms.

For example, a patient presents with pleural effusion resulting from disease progression of metastasis to lungs. The event term should be reported as “pleural effusion” instead of disease progression. If a patient experienced a fatal multiorgan failure due to disease progression, the term “multiorgan failure” should be reported as the SAE with death as outcome instead of reporting “fatal disease progression” or “death due to disease progression”.

9.4.2. Death

Death is an outcome and not usually considered an event. If the only information available is death and the cause of death is unknown, then the death is reported as an event, eg, “death”, “death of unknown cause”, or “death unexplained”.

9.5. Prompt Reporting of Serious Adverse Events

9.5.1. Timeframes for Submitting Serious Adverse Events

SAEs will be reported promptly (within 24 hours) to the sponsor or designee as described in [Table 5](#) once the investigator determines that the AE meets the protocol definition of an SAE.

Table 5: Timeframes and Documentation Methods for Reporting Serious Adverse Events to the Sponsor or Designee

Type of SAE	Initial SAE Report	Document	Follow-up SAE and AE of Special Interest Report	Reporting Method
All SAEs	Within 24 hours of first knowledge of the SAE	SAE report	As expeditiously as possible	Email or fax SAE form or Pregnancy form

Abbreviations: AE, adverse event; SAE, serious adverse event.

9.5.2. Completion and Transmission of the Serious Adverse Event Report

Once an investigator becomes aware that an SAE has occurred in a patient, he/she will report the information to the sponsor within 24 hours as outlined in [Section 9.5.1](#). The SAE Report will always be completed as thoroughly as possible with all available details of the event and forwarded to the sponsor or designee within the designated timeframes.

If the investigator does not have all information regarding an SAE, he/she is not to wait to receive additional information before notifying the sponsor or designee of the SAE and completing the form. The form will be updated when additional information is received.

The investigator will always provide an assessment of causality at the time of the initial report as described in [Section 9.1.3](#).

The sponsor will provide contact information for SAE receipt.

9.5.3. Regulatory Reporting Requirements for Serious Adverse Events

The investigator will promptly report all SAEs to the sponsor in accordance with the procedures detailed in [Section 9.5.2](#). The sponsor has a legal responsibility to notify, as appropriate, both the local regulatory authority and other regulatory agencies about the safety of a product under clinical investigation.

The investigator, or responsible person according to local requirements, will comply with the applicable local regulatory requirements related to the reporting of SAEs to regulatory authorities and the IRB/IEC.

All suspected unexpected serious adverse reactions (as defined in [Section 9.6](#)) will be submitted to all applicable regulatory authorities and investigators for pamiparib studies.

When a study center receives an initial or follow-up safety report or other safety information (eg, revised Investigator's Brochure) from the sponsor, the investigator or designated responsible person is required to promptly notify his/her IRB or IEC. The investigator should place copies of Safety Reports from the sponsor in the Investigator Site File.

9.6. Suspected Unexpected Serious Adverse Reactions and Expedited Reporting

A suspected unexpected serious adverse reaction is a serious adverse reaction that is both unexpected (ie, not present in the product's Reference Safety Information in the Investigator's Brochure) and assessed as related to pamiparib either by the investigator or the sponsor. The sponsor will promptly assess the expectedness for all SAEs against the list of expected serious adverse reactions in the Reference Safety Information and expeditiously submit suspected unexpected serious adverse reactions to regulatory authorities, investigators, IRBs, and IECs based on applicable legislation.

9.7. Pregnancy Reporting

If the partner of a patient becomes pregnant while receiving pamiparib or within 6 months after completion of the last dose of pamiparib, a pregnancy report form is required to be completed and expeditiously submitted to the sponsor to facilitate outcome follow-up. Information on the status of the mother and child will be forwarded to the sponsor. Generally, follow-up will be no longer than 6 to 8 weeks following the estimated delivery date. Any premature termination of the pregnancy will be reported.

While pregnancy itself is not considered to be an AE or SAE, any pregnancy complication or elective termination of a pregnancy for medical reasons will be recorded as an AE or SAE.

An abortion, whether accidental, therapeutic, or spontaneous, should be always reported as an SAE. Similarly, any congenital anomaly/birth defect in a child born to a patient exposed to pamiparib should be recorded and reported as an SAE.

10. STATISTICAL CONSIDERATIONS AND ANALYTICAL PLAN

Details of the statistical analyses will be included in the Statistical Analysis Plan.

10.1. Analysis Sets

- Safety Analysis Set: includes all patients enrolled into the study who receive any dose of pamiparib. The Safety Analysis Set will be used for all safety analyses.
- Efficacy-Evaluable Analysis Set (ORR Assessment in Cohort 1 of [Table 2](#)): includes all patients in the Safety Analysis Set who had measurable disease at baseline and at least 1 postbaseline tumor assessment, unless they permanently discontinue pamiparib or the study early due to clinical progression or death before tumor assessment. The Efficacy-Evaluable Analysis Set is the primary analysis set for tumor response analysis.
- PSA-Evaluable Analysis Set (PSA Response Rate Assessment in Cohorts 1 and 2 of [Table 2](#)): includes all patients in the Safety Analysis Set as per Inclusion Criterion 7 at baseline (≥ 3 rising

PSA levels with ≥ 1 week between determinations and screening PSA ≥ 2 $\mu\text{g/L}$) and who had at least 1 postbaseline PSA measurement, unless they permanently discontinue pamiparib or the study early due to clinical progression or death before completed PSA assessment.

- PK Analysis Set: includes all patients who received pamiparib and for whom valid pamiparib PK parameters can be estimated.

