5.6.4. Patient Discontinuation From Study (End of Study for an Individual Patient)

Premature discontinuation from the study (without EOT and any follow-up visits) will occur under the following circumstances:

- Patient withdrew consent for study participation

- Patients may voluntarily withdraw consent from the study at any time
- Investigator's discretion
- Lost to follow-up
 - Lost to follow-up should be recorded as such in the eCRF
 - The investigator should show due diligence by documenting in the source documents steps taken to contact the patient ([Section 5.6.3](#))
- Death
- Study termination by sponsor
- Other, as per the discretion of the sponsor or health authority

When a patient withdraws before the end of the study, the reason for withdrawal should be recorded in the source document and eCRF. Patients who withdraw from the study will not be replaced.

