10.2. Efficacy Analyses

10.2.1. Primary Efficacy Endpoint Analyses

The primary endpoints of the study include ORR by IRC assessment in CTC-HRD-positive patients with measurable disease and PSA response rate in CTC-HRD-positive patients with or without measurable disease per PCWG3 criteria.

ORR is defined as the proportion of patients with best objective response of CR or PR confirmed at a subsequent timepoint ≥ 4 weeks later by IRC assessment. Patients without tumor assessment are considered non-responders.

ORR is assumed as 35% for pamiparib and estimated as 15% for historical control in the study population. The null and alternative hypotheses are set as follows:

$$H_0: \text{ORR} = 15\%$$

$$H_a: \text{ORR} > 15\%$$

PSA response rate is defined as the proportion of patients with PSA decline $\geq 50\%$ from baseline (confirmed by a second PSA value ≥ 3 weeks later).

PSA response rate is assumed as 50% for pamiparib and estimated as 30% for historical control in the study population. The null and alternative hypotheses are set as follows:

$$H_0 : \text{ORR} = 30\%$$

$$H_a : \text{ORR} > 30\%$$

Binomial exact tests will be performed for above hypotheses in the Efficacy-Evaluable Analysis Set. Two-sided binomial exact 95% CI of response rate will be constructed to assess the precision of the estimates.

To control the overall study type-I error rate, ORR and PSA response rate will be tested sequentially. If the ORR test shows significance at 1-sided 0.025 significance level, PSA response rate will be tested at a 1-sided 0.025 significance level.

The primary efficacy analyses will be conducted when mature response data have been observed, which will be determined by the sponsor.

A sensitivity analysis of response rate will be conducted using the Safety Analysis Set.

ORR and PSA response rate will be summarized in the specified subgroups: age group (< 65 versus ≥ 65), race, geographic region, ECOG performance status, BRCA1/2-mutant status, and number of prior lines of therapy.

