## 6 STATISTICAL METHODS

### 6.1 ANALYSIS POPULATIONS

- Safety Analysis Set (SAF): includes all patients enrolled in the study who receive any dose of pamiparib. The Safety Analysis Set will be used for all safety analyses.
- Efficacy-Evaluable Analysis Set (ORR Assessment in Cohort 1 of Table 1): includes all patients in the Safety Analysis Set who had measurable disease at baseline and at least 1 postbaseline tumor assessment, unless they permanently discontinue pamiparib or the study early due to clinical progression or death prior to tumor assessment. A similar analysis population will exist for exploratory analyses of Cohort 3.
- Efficacy-Evaluable Analysis Set (PSA Response Rate Assessment in Cohorts 1 and 2 of Table 1): includes all patients in the Safety Analysis Set as per Inclusion Criterion 7 at baseline ( $\geq 3$  rising PSA levels with  $\geq 1$  week between determinations and screening PSA  $\geq 2$   $\mu\text{g/L}$ ) and who had at least 1 postbaseline PSA measurement, unless they permanently discontinue pamiparib or the study early due to clinical progression or death before completed PSA assessment. A similar analysis population will exist for exploratory analyses of Cohorts 3 and 4.
- PK Analysis Set: includes all patients who received pamiparib and contributed at least one plasma concentration.

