**Table 2 Primary and Secondary Efficacy Endpoint Analysis Populations**

	Efficacy Endpoint	Analysis Population
Primary	ORR by IRC	Efficacy-Evaluable Analysis Set (ORR Assessment in Cohort 1)
	PSA Response	Efficacy-Evaluable Analysis Set (PSA Response Rate Assessment in Cohorts 1 and 2)
Secondary	DOR by IRC	Efficacy-Evaluable Analysis Set (ORR Assessment in Cohort 1), those w/objective response per IRC
	ORR by INV	Efficacy-Evaluable Analysis Set (ORR Assessment in Cohort 1)
	Time to Objective Response by INV	Efficacy-Evaluable Analysis Set (ORR Assessment in Cohort 1), those w/confirmed objective response per INV
	Clinical Benefit Rate by INV	Efficacy-Evaluable Analysis Set (ORR Assessment in Cohort 1)
	Time to PSA Response	Efficacy-Evaluable Analysis Set (PSA Response Rate Assessment in Cohorts 1 and 2), those w/confirmed PSA response
	Duration of PSA Response	Efficacy-Evaluable Analysis Set (PSA Response Rate Assessment in Cohorts 1 and 2), those w/confirmed PSA response
	Time to PSA Progression	Safety Analysis Set (Cohorts 1 and 2)
	Time to SSE	Safety Analysis Set (Cohorts 1 and 2)
	rPFS by IRC	Safety Analysis Set (Cohorts 1 and 2)
OS	Safety Analysis Set (Cohorts 1 and 2)	

Abbreviations: DOR = duration of response; INV = investigator; IRC = independent review committee; ORR = objective response rate; OS = overall survival; PSA = prostate-specific antigen; rPFS = radiographic progression-free survival; SSE = symptomatic skeletal event.

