### 6.4.1 Primary Efficacy Endpoints

#### Objective Response Rate (ORR) by IRC

ORR is defined as the proportion of patients with a best objective response of CR or PR confirmed at a subsequent timepoint  $\geq 4$  weeks later. For this primary efficacy endpoint, the tumor assessments will be performed by the IRC and will be summarized for the Efficacy-Evaluable Analysis Set (ORR Assessment in Cohort 1).

ORR (number and proportion of patients) will be presented along with its Clopper-Pearson 2-sided 95% confidence interval. The number and proportion of patients who achieve an unconfirmed best objective response of CR or PR will also be summarized.

ORR will be tested against a historical control ORR, and the null and alternative hypotheses are as follows:

$$H_0: \text{ORR} = 15\%$$

$$H_a: \text{ORR} > 15\%$$

A binomial exact test will be performed for the above hypotheses at a one-sided 0.025 significance level. If the result for ORR is statistically significant, ie, one-sided p-value  $< 0.025$ , then the primary efficacy endpoint of PSA response rate will be tested for statistical significance.

If the Efficacy-Evaluable Analysis Set (ORR Assessment in Cohort 1) is not equivalent to the Safety Analysis Set for Cohort 1, a sensitivity analysis of ORR will be conducted on the Safety Analysis Set for Cohort 1. The sensitivity analysis will be carried out in the Safety Analysis Set. Patients without postbaseline tumor assessment will be considered as non-responders in the Safety Analysis Set and will be classified as “not assessed.”

Waterfall plots will be provided for the maximum tumor shrinkage from baseline based on the sum of diameters of all target lesions.

Subgroup analyses for ORR will be performed as described in Section [6.4.3](#).

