#### PSA Response Rate

PSA response rate is defined as the proportion of patients with a PSA decline  $\geq 50\%$  from baseline confirmed by a second PSA value  $\geq 3$  weeks later. For this primary efficacy endpoint, the PSA assessments will be summarized for the Efficacy-Evaluable Analysis Set (PSA Response Rate Assessment in Cohorts 1 and 2).

PSA response rate (number and proportion of patients) will be presented along with its Clopper-Pearson 2-sided 95% confidence interval. The number and proportion of patients who achieve an unconfirmed PSA decline  $\geq 50\%$  from baseline will also be summarized.

If the primary efficacy endpoint of ORR is statistically significant, PSA response rate will be tested against a historical control PSA response rate, and the null and alternative hypotheses are as follows:

$H_0$ : PSA response rate = 30%

$H_a$ : PSA response rate > 30%

A binomial exact test will be performed for the above hypotheses at a one-sided 0.025 significance level. If the result for PSA response rate is statistically significant, ie, one-sided p-value < 0.025, then PSA response rate will be considered statistically significant. Note that if the primary efficacy endpoint of ORR is not statistically significant, then no claims of statistical significance can be made for the primary efficacy endpoint of PSA response rate.

If the Efficacy-Evaluable Analysis Set (PSA Response Rate Assessment in Cohorts 1 and 2) is not equivalent to the Safety Analysis Set for Cohorts 1 and 2, a sensitivity analysis of PSA response rate will be conducted on the Safety Analysis Set for Cohorts 1 and 2. The sensitivity analysis will be carried out in the Safety Analysis Set. Patients without postbaseline tumor assessment will be considered as non-responders in the Safety Analysis Set and will be classified as “not assessed.”

Subgroup analyses for PSA response rate will be performed as described in Section [6.4.3](#).

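### Both primary response tests drop treated patients who have no postbaseline assessment, which can push type I error above 0.025 if the benchmarks are all-treated rates

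*Protocol*

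**What the plan says.** **Who is in the primary sets.** Protocol 10.1 limits the ORR set to treated patients with measurable disease who have "at least 1 postbaseline tumor assessment, unless they permanently discontinue pamiparib or the study early due to clinical progression or death before tumor assessment". SAP 6.1 keeps the rule: the set "includes all patients in the Safety Analysis Set who had measurable disease at baseline and at least 1 postbaseline tumor assessment", with the same exception. The PSA set (Cohorts 1 and 2) has a parallel condition: Inclusion Criterion 7 at baseline and at least one postbaseline PSA value, again except for early clinical progression or death.

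**Which set decides the tests.** Protocol 10.2.1, SAP Table 2 and SAP 6.4.1 run both primary exact binomial tests in these evaluable sets.

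**Non-responder rules.** For ORR, Protocol 10.2.1 says: "Patients without tumor assessment are considered non-responders". It has no counterpart for PSA. In SAP 6.4.1, if the two sets differ, "a sensitivity analysis of ORR will be conducted on the Safety Analysis Set for Cohort 1", and unassessed patients count as non-responders there. The PSA part of SAP 6.4.1 reuses the same sentence: "Patients without postbaseline tumor assessment will be considered as non-responders in the Safety Analysis Set".

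**Benchmarks.** Protocol 10.2.1 gives the ORR null as "estimated as 15% for historical control in the study population" and uses the same form for the 30% PSA null. Neither has a source or a denominator.

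**The concern.** Membership of both primary sets depends on something observed after treatment starts. A treated patient who withdraws consent or is lost before his first scan or PSA value leaves the denominator. Protocol 5.6.4 describes these exits: "Premature discontinuation from the study (without EOT and any follow-up visits) will occur under the following circumstances". It also says such patients are not replaced.

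The ORR non-responder sentence in Protocol 10.2.1 is narrowed as a result. Inside the evaluable set it can reach only the progression and death cases, because the other unassessed patients have already been removed. For PSA the point is by analogy, since no such sentence exists.

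A patient with no postbaseline value cannot have a recorded confirmed response, so removing him can raise the observed rate but never lower it. The rate is compared with a fixed benchmark and there is no control arm in which similar exclusions might offset this. At stake is whether the one-sided 0.025 level holds for the population that was treated.

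There is also a plain wording error. The PSA sensitivity analysis defines non-response by a missing tumor assessment. Read literally, a confirmed PSA responder without a scan becomes a non-responder, and a patient with a scan but no PSA value is not covered.

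**Working it through.** **Inputs.** One-sided alpha 0.025, exact binomial (SAP 6.4.1). ORR: null 15%, alternative 35%, n = 50, power 88%. PSA: null 30%, alternative 50%, n = 80, power 95% (Protocol 10.2.1 and 10.6). The documents give no exclusion rate, so it is varied.

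**Step 1: reproduce the plan.** The critical value c(n) is the smallest count with upper-tail probability below 0.025 under the null p0.
- ORR: reject at 14/50 or more; size 0.0132, power 0.884.
- PSA: reject at 33/80 or more; size 0.0211, power 0.954.

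Both stated powers reproduce.

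**Step 2: type I error with exclusions.** Assume p0 is the rate among all N treated patients, each patient is excluded with probability f, and every excluded patient is a non-responder. The rate among evaluable patients is then p0/(1 − f), and

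error(f) = Σ over m of P[Bin(N, f) = m] × P[Bin(N − m, p0/(1 − f)) ≥ c(N − m)].

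| Expected exclusions | ORR | PSA (taken alone) |
|---|---|---|
| 0% | 0.013 | 0.021 |
| 2% | 0.017 | 0.027 |
| 4% | 0.022 | 0.036 |
| 5% | 0.024 | 0.041 |
| 6% | 0.026 | 0.046 |
| 10% | 0.034 | 0.075 |

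The error equals 0.025 at f = 5.33% for ORR and f = 1.42% for PSA.

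**Step 3: a fixed number excluded.** The evaluable rate is p0 × N/(N − m).
- One excluded: cut-offs stay at 14/49 and 33/79; error 0.0130 (ORR) and 0.0208 (PSA), no excess.
- Two excluded: cut-offs drop to 13/48 and 32/78; error 0.0295 (ORR) and 0.0352 (PSA).

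The jump is a step in the critical value.

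**Step 4: weaker assumptions.** An excluded patient has no recorded response, but he might have responded had he been assessed. Let that latent rate be r times the null rate, so the evaluable rate is p0(1 − f·r)/(1 − f).
- r = 0.5: 0.020 (ORR) and 0.029 (PSA) at 5%; 0.024 and 0.040 at 10%. Only PSA exceeds 0.025.
- r = 1 (evaluability unrelated to response): 0.016 and 0.019 at 10%. No excess.
- Null true among evaluable patients, 0 to 8 excluded: at most 0.0218 (ORR) and 0.0249 (PSA). No excess.

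**Step 5: all treated patients in the denominator.** With the null holding for all treated patients, size returns to 0.0132 and 0.0211 whatever the amount of missing data.

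**The case against.** **The benchmark denominator is unknown.** If 15% and 30% are evaluable-set rates, the current tests keep their level, and an all-treated test becomes conservative: size 0.0085 (ORR) and 0.0097 (PSA) at 5% missing. This stands as a condition on the size of the problem. It does not remove it, because the plan gives the reader no way to tell which case applies.

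**The excluded group is small.** Progression and death cases are kept. Protocol 5.6.2 keeps patients who stop drug for an adverse event under scan and PSA follow-up, and Appendix 1 schedules PSA, CT and bone scan at the End-of-Treatment Visit. PSA is due every 4 weeks, so PSA exclusion generally means leaving within about a month or missing every draw. All true; it bears on the likely value of f. SAP 8 reports that most of the 13 enrolled patients had no postbaseline tumor assessment. It gives no reasons, so this is not an exclusion rate, but it shows that unscanned patients were not a remote case.

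**PSA is gated by ORR.** Under SAP 6.2.4, if both nulls hold, a false PSA claim cannot occur more often than ORR passes. The 1.4% figure is for the PSA test alone and should be read that way.

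**The thresholds depend on the set-up.** If 50 and 80 are evaluable counts instead of treated counts, the crossings are 7.6% and 1.2%.

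**An all-treated analysis is already planned.** It would reveal a discrepancy, but it does not decide the test.

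**Conclusion.** The concern holds. Both deciding tests condition on a postbaseline assessment, and for ORR this narrows the protocol's own non-responder rule.

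The numerical consequence rests on two assumptions: the benchmarks are all-treated rates, and excluded patients are non-responders. Under both, with 50 and 80 treated patients, the 0.025 level is passed at about 5.3% expected exclusions for ORR and 1.4% for PSA alone, or with exactly two patients excluded in either test. If the benchmarks apply to evaluable patients, or evaluability is unrelated to response, there is no excess.

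The PSA wording error in SAP 6.4.1 stands regardless of these assumptions. This is a cheap improvement to the plan. SAP 8 says no efficacy analysis will be conducted, so no result of this trial is affected.

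**What to change.** - In the Synopsis, Protocol 10.1 and 10.2.1, and SAP 6.1, Table 2 and 6.4.1, delete the postbaseline-assessment condition and its exception from both primary sets. Keep the baseline conditions (measurable disease for Cohort 1; Inclusion Criterion 7 for PSA), which are fixed before treatment.
- Count every treated patient in these sets without a confirmed response as a non-responder, and say so for PSA as well as ORR.
- Keep the present evaluable sets as supportive analyses.
- In the PSA part of SAP 6.4.1, make the non-responder rule refer to a missing postbaseline PSA assessment.
- State in the sample-size section that 88% and 95% power assume 35% and 50% are all-treated rates.
- Useful additions: give the denominator of the 15% and 30% benchmarks, and name the PSA set for the PSA test in Protocol 10.2.1, which now names only the Efficacy-Evaluable set for both tests.

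**Cost.** No new data are needed, though the headline rate may be lower. If 35% and 50% are all-treated rates, sample size and power stand. If they hold only among evaluable patients, the all-treated rates are 0.35(1 − f) and 0.50(1 − f):

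| Missing | Power at n = 50 / 80 | Smallest n for 88% / 95% |
|---|---|---|
| 2% | 86% / 93% | 51 / 86 |
| 5% | 82.5% / 89% | 53 / 101 |
| 10% | 75% / 78% | 63 / 136 |

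Exact-test power is saw-toothed, so these sample sizes are minimum values. On the same assumption the present evaluable-set test keeps 88%/94% at 5% and 86%/93% at 10%.
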